1.1 TIME AND EVENTS SCHEDULES

| Table 1: Time and | Events Schedule |
|-------------------|------------------------|
|-------------------|------------------------|

| Assessment | Screen (D-56+7 ^e to D0) | A | Cycle | | Cycl | e 2-3 | Additional Treatments | Follow- up/End of study |
|--------------------------------|--|----|-------|------|---------|--------|--------------------------|-------------------------------|
| | | D1 | D8 | D15± | D22 | D43 | Every $21 \pm$ | Every 28 ± 3 |
| | | | ± 2 | 2 | ± 3 | ± 3 | 3 day | days after |
| | | | | | | | 5 | final |
| | | | | | | | | treatment for |
| | | | | | | | | 6 Months |
| Signed Informed Consent | Х | | | | | | | |
| HAAH assessment ^a | Х | | | | | | | |
| Demographics | Х | | | | | | | |
| Medical/Oncology | Х | | | | | | | |
| History | | | | | | | | |
| Tumor Burden | Х | | | | | | | |
| Evaluation ^d | | | | | | | | |
| Baseline Signs and | Х | | | | | | | |
| Symptoms | | | | | | | | |
| Physical Examination | Х | | | | | | | Х |
| Symptom-Directed | | Х | Х | Х | Х | Х | Х | |
| Physical Examination | | | | | | | | |
| Vital Signs | Х | Х | Х | Х | Х | Х | Х | Х |
| ECOG Performance Score | Х | Х | Х | Х | Х | Х | Х | Х |
| ECG | Х | Х | | | Х | Х | Х | Х |
| PSA | Х | Х | | | Х | X X | X X | Х |
| Hematology ^b | Х | Х | Х | Х | Х | | | |
| Chemistry ^b | Х | Х | Х | Х | Х | Х | Х | |
| Coagulation, CH50 ^b | Х | Х | Х | Х | Х | Х | Х | |
| Study Treatment | | Х | | | Х | Х | Х | |
| administration | | | | | | | | |
| Physician Administration | | Х | Х | | Х | Х | Х | |
| Site Assessment | | | | | | | | |
| Immunologic Blood | | Х | | | Х | Х | Х | Х |
| Collection ^c | | | | | | | | |
| Cohort enrollment | | | | | Х | | | |
| evaluation | | | | | | | | |
| Concomitant Medications | | Х | Х | Х | Х | Х | Х | Х |
| Collection | | | | | | | | |
| Adverse Events | | Х | Х | Х | Х | Х | Х | Х |
| Assessments ^f | FCO | | | | | | DGA | |

Abbreviations: ECG: electrocardiogram; ECOG: Eastern Cooperative Oncology Group; PSA: prostate-specific antigen

- a HAAH assessment: following informed consent, archived prostate tumor tissue and patient serum will be tested for the expression of HAAH. Only patients who test positive for HAAH expression in archived tumor tissue (if available) or fresh serum may be continued in the study. HAAH assessments are not subject to the 56-day screening window and are valid for 6 months. Patients who are negative for HAAH may be followed for 6 months and if PSA rises over that period time, they can enroll in the study provided that tissue or fresh serum is positive for HAAH
- b Biochemical testing (chemistry, complete blood count, coagulation, and total complement CH50,) to be obtained within 14 days prior to study drug administration if screening period is between 3 and 8 weeks. PSA levels are also to be evaluated at screening and within 14 days prior to study drug administration if screening period is between 3 and 8 weeks.
- c Immunologic blood collection: to be taken pre-dose on the day of study drug administration (Day 1) and every 21 days thereafter. Following the 9th dose (or last dose otherwise), PSA levels and other assessments will be followed on a monthly basis for 6 months. Patients with evidence of progression and declining HAAH immune parameters will have the option of resuming therapy on the study protocol.

- d Baseline radiological tumor burden evaluation consists of a baseline pelvic MRI or CT scan in addition to bone scan. These studies will need to be performed within 56 days (+ 7 days) prior to the start of the study.
- e Patients that have a delay in screening beyond 56-days may be re-screened for randomization.
- f Adverse events that occur post patient receiving study drug. Should Adverse event occur prior to patient receiving study drug they will be captured as Medical History.

2. TERMS, ACRONYMS, ABBREVIATIONS

| Term | Definition |
|-------------|--|
| 7-ADD | 7-amino actinomycin D |
| ADL | Activities of daily living |
| AE | Adverse event |
| ALT | Alanine aminotransferase |
| AP | Alkaline phosphatase |
| APC | Antigen-presenting cells |
| ASR | Administration site reaction |
| AST | Aspartate aminotransferase |
| °C | Celsius |
| CBC | Complete blood count |
| CFR | Code of Federal Regulations |
| CFSE | Carboxyfluorescein succinimidyl ester |
| CH-50 | Total complement activity |
| CpG | 5'-c-phosphate-G-3'(a DNA sequence) |
| CTL | Cytotoxic CD8+ T-lymphocytes |
| DLT | Dose-limiting toxicity |
| DNA | Deoxyribonucleic acid |
| ECG | Electrocardiogram |
| ECOG | Eastern Cooperative Oncology Group |
| eCRF | Electronic case report form |
| EDC | Electronic data capture |
| ELISA | Enzyme-linked immunosorbent assay |
| EOS | End of study |
| FDA | Food and Drug Administration (U.S.) |
| GMT | Geometric mean titer |
| gpD | Head DNA stabilization protein of Bacteriophase lambda |
| НААН | Human aspartyl-asparaginyl-β-hydroxylase |
| hMTS | 3M® hollow microstructured transdermal system |
| ICF | Informed consent form |
| IgG | Immunoglobulin G |
| IND | Investigational New Drug |
| IRB | Institutional review board |
| irRC | Immune-related response criteria |
| kDa | Kilodalton |
| LVEF | Left ventricular ejection fraction |

| Term | Definition |
|--------------------|--|
| MACS | Magnetic activated cell sorting |
| MHC | Major histocompatibility complex |
| mL | Milliliters |
| M0 | Non-metastatic cancer |
| M1 | Metastatic cancer |
| MTD | Maximum tolerable dose |
| NCI-CTCAE V4.03 | National Cancer Institute Common Terminology Criteria for Adverse Events V 4.03 |
| PBMC | Peripheral blood monocytes |
| SNS-301 | HAAH bacteriophage lambda constructs: HAAH-1 λ |
| PSA | Prostate-specific antigen |
| RP | Radical prostatectomy |
| RP2D | Recommended phase 2 dose |
| SAE | Serious adverse event |
| WOCBP | Women of child-bearing potential |

3. INTRODUCTION

3.1 Primary Disease and Study Treatment Information

Human aspartyl-asparaginyl- β -hydroxylase (HAAH), also known as aspartate- β -hydroxylase, is an ~86 kDa type 2 transmembrane protein that belongs to the α -ketoglutarate-dependent dioxygenase family [1]. It is a highly conserved enzyme, which catalyzes the hydroxylation of aspartyl and asparaginyl residues in epidermal growth factor-like domains of proteins including Notch and homologs [2]. HAAH was initially identified in a novel screen to identify cell surface proteins up-regulated in liver cancer. It has subsequently been detected in a diverse array of solid and blood cancers, including: liver, bile duct, brain, breast, colon, prostate, ovary, pancreas, and lung cancers as well as leukemia. HAAH is not found in significant quantities in normal tissue or in proliferative disorders.

Over-expression of HAAH has been demonstrated to be sufficient to induce cellular transformation, increase cellular proliferation and cellular motility and suppression of HAAH expression (small interfering ribonucleic acid) or neutralized activity (monoclonal antibodies) returns cancer cells to a normal phenotype. In cancer cells, it has been shown to be translocated to the cellular surface where it is not normally located. Because HAAH is an embryonic antigen, and as such presents self-antigen tolerance, it is relatively difficult to elicit a robust immune response against it. Thus, we posited that effective priming of antigen-presenting cells (APC) by HAAH antigen is an essential step to overcome tolerance. Indeed, *in vitro* activation of dendritic cells with HAAH, prior to re-administration to patients has shown promising results for liver cancer therapy [3]. Unfortunately, this process is cumbersome, expensive, time consuming and impractical for mass scale immunotherapy.

Bacteriophage display is a simple, inexpensive and practical way of achieving favorable presentation of peptides to the immune system. The phage contains deoxyribonucleic acid (DNA) fragments that present the phage CpG motifs, which are known to stimulate the innate immune response and activate the major histocompatibility class (MHC) class II pathway in APC. Previous findings have revealed that recombinant bacteriophage can prime strong CD8+ T-lymphocyte (CTL) responses both in vitro and in vivo against epitopes displayed in multiple copies on their surface [4], activate T-helper cells [5] and elicit the production of specific antibodies [6, 7] all normally without adjuvant. Thus we have selected bacteriophage as a platform for eliciting anti-HAAH immune responses. Bacteriophage are ubiquitous and essentially innocuous to humans, however, as an added safety mechanism, they may be neutralized rendering them non-infective to host bacteria while retaining their immunostimulant properties. Once neutralized, the bacteriophage effectively becomes a nanoparticle, for enhanced delivery of protein fragments to APC.

We have designed a bacteriophage lambda system to display HAAH peptides fused at the C-terminus of the head protein gpD of phage lambda. The phage carry 200-300 copies of the gpD protein on their head and thus display many copies of an approximately 25 kDa molecular weight fragment of HAAH on their surface. The drug substance is one of these HAAH bacteriophage lambda constructs: HAAH-1 λ (SNS-301).

3.2 Previous Non-Clinical Experience

Nonclinical studies have focused on the immunogenicity and efficacy of the HAAH Nanoparticle Vaccine in rodent models. Nonclinical toxicology studies have been completed and are described below.

The nonclinical data generated to date include:

- Demonstration of immunogenicity in mice and rats
- Demonstration of dose response to both amount of vaccine and number of doses
- Demonstration of both humoral and cellular immunity
- Demonstration of enhanced immunogenicity for intradermal compared to intramuscular immunization
- Efficacy data in three rodent tumor models, including solid tumors and metastases
 - Inhibition of solid tumor growth and metastases with the mouse hepatocellular carcinoma cell line, BNLT3
 - Inhibition of solid tumor growth, lung metastases and mortality with the mouse breast cancer cell line, 4T1
 - \circ Inhibition of metastases with the rat prostate cancer cell line, MLLB-2

The data listed above have been generated in three laboratories, which provide corroboration of the nonclinical observations in multiple environments and with multiple technical staff. It is important to note that there has been no local reactogenicity or adverse events (AEs) associated with the administration of multiple doses of the HAAH Nanoparticle Vaccine in mice and rats. These vaccines are immunogenic, show efficacy in three tumor model systems and are safe in the doses given to rodents. In total, the data strongly support the potential utility of the HAAH-1 λ vaccine for the immunotherapy of cancer.

It is anticipated that the HAAH Nanoparticle Vaccine will also prove to be safe in humans. Bacteriophages are ubiquitous in our environment. All humans are constantly exposed to large numbers of bacteriophage with no apparent harm. The relatively low dose and dose frequency of a vaccine as compared to other cancer drugs, both chemical and biological, also predict that these materials should be quite safe in human subjects.

Panacea has conducted a repeated dose study in rats that assessed the toxicity of the SNS-301 (previously named PAN-301-1) HAAH nanoparticle vaccine when administered intradermally at the same three dose levels $(2 \times 10^{10}, 1 \times 10^{11} \text{ and } 3 \times 10^{11} \text{ particles})$ and same dose schedule (3 doses given at 21 day intervals) as proposed for this human study, followed by 2 week and 4-week recovery periods. These dose levels were chosen based on demonstrated immunogenicity and efficacy in the animal models described above. The conclusions of the study were that treatment with SNS-301 at doses up to 3 x 10^{11} particles had no effect on mortality, physical examinations, cage-side observations, dermal Draize observations, body weights or body weight changes, food consumption, body temperature, ophthalmologic observations, gross pathology, absolute and relative organ weights, hematology or clinical chemistry. A slightly prolonged but non-adverse PT time in males given $\geq 1 \ge 10^{11}$ particles and females given $3 \ge 10^{11}$ particles persisted through the first recovery period (2 weeks post-3rd injection). The prolonged PT time resolved in males by the second recovery period (4 weeks post-3rd injection) but remained minimally prolonged in females given 3 x 10¹¹ particles. Test article-related microscopic findings were present in the injection site in animals given > 1 x 10^{11} particles and consisted of mild or moderate mononuclear or mixed inflammatory cell infiltrates in the dermis and/or subcutis. These findings were considered non-adverse and resolved during recovery. Additionally, the SNS-301 vaccine demonstrated a significant antibody response that was dependent on both the dose level and number of doses administered.

These toxicology results demonstrate safety of the SNS-301 HAAH nanoparticle vaccine and support the planned multiple dose Phase 1 study of the HAAH Nanoparticle Vaccine in humans described in this protocol.

3.4 Study Rationale

Oncology trials frequently employ dose-escalation using a 3+3 schema; it is considered standard practice for determining the MTD of a particular study treatment in humans. The starting dose for such studies is usually calculated from the results of toxicology studies, which are often not performed in humans [8]. In this study, the starting dose and the subsequent dose escalations were determined from the results of a repeated dose toxicology study conducted in rats that evaluated the same 3 intradermal doses and dose frequency for the SNS-301 as proposed here. Only minimal toxicologic effects were observed in the animals at the higher two dose levels and these were resolved through the 2- and 4-week recovery periods (see Section 3.2).

The selection rationale for the specific dose levels proposed for this study is based on the in vivo results of this range of doses in mice and rats that have shown both immunogenicity and efficacy of the SNS-301 vaccine. The vaccine has demonstrated immunogenicity in rats by IgG antibody response to recombinant HAAH and to the recombinant bacteriophage HAAH- 1λ drug substance at each dose level, 2×10^{10} , 1×10^{11} and 3×10^{11} particles. This antibody response is both dose level-dependent and dose number-dependent. In mice, dose levels of approximately 2×10^{10} to 3×10^{11} particles have also demonstrated immunogenicity in a similar dose level- and dose number-response manner in multiple studies. Furthermore, SNS-301 vaccine doses up to 3×10^{11} particles have demonstrated inhibition of solid tumor growth and metastases in in vivo mouse tumor models with the mouse hepatocellular carcinoma cell line, BNLT3, and with the mouse breast cancer cell line, 4T1 and have demonstrated inhibition of metastases in a rat tumor model with the rat prostate cancer cell line, MLLB-2.

The dose-escalation phase will be conducted in patients with biochemically relapsed prostate cancer because this is a cancer that generally takes a long time to develop. Further, archived patient tumor tissue will be tested for the HAAH epitope before enrollment into the study; patients who do not test positive for the HAAH epitope in archived tissue or fresh serum

sample will not be entered into the treatment phase as they are not deemed suitable candidates for the HAAH vaccine. The 21-day treatment phase will allow the patient sufficient time to recover from any adverse effects of the vaccine before the next dose. It is anticipated that the SNS-301 will lead to the development of active anti-HAAH immunity with consistent polyclonal anti-HAAH antibody titers in addition to development of anti-HAAH T-cells. This is further supported by our current data from patients treated up to now. Based on this, a decision has been made to limit the total number of injections to 9, which accounts for 6 months of treatment with an additional 6 months of follow up, with monthly measurement of PSA levels and anti-HAAH immunity parameters. Patients who, at the time of this amendment, have received more than 9 injections, will cease treatment at the time of their last injection when this amendment goes into effect and will also be followed for 6 months, as will patients whose disease progression leads to treatment stoppage before 1 year. Patients with evidence of progression and declining HAAH immune parameters have the option of resuming therapy on the study protocol in the 6 month follow up period. All patients are eligible for enrollment in the expanded access protocol after study closure.

4. Study Objectives and Endpoints

4.1 Study Objectives

4.1.1 Primary

• To determine the maximum tolerated dose (MTD) of SNS-301 based on the incidence of dose-limiting toxicities (DLT) and the maximum administered dose of SNS-301, when administered every 21 days in patients with biochemically relapsed prostate cancer

4.1.2 Secondary

• To assess the overall safety of SNS-301

4.2 Study Endpoints

4.2.1 Primary

- To determine the MTD
- Determine the recommended Phase 2 dose (RP2D) if different than the MTD
- Determine the DLTs associated with SNS-301

4.2.2 Secondary

- Incidence of administration site reactions
- Biochemical safety and tolerability
- Geometric mean titers of anti-HAAH antibodies by dose
- Antigen-specific CTL responses by dose
- Production of B cell and T cell response of interest

4.2.3 Clinical secondary endpoints

- Change in the prostate-specific antigen (PSA) velocity
- Reduction in the PSA doubling time from pre-baseline

4.2.4 Pharmacodynamic secondary endpoints

- Duration of antigen-specific anti-HAAH antibody titers
- Changes in the amplitude or duration of the production of anti-HAAH antibodies
- Correlation of anti-HAAH titers and serum HAAH levels

5. INVESTIGATIONAL PLAN

This is a Phase I, open-label, study of SNS-301, an HAAH-directed nanoparticle vaccine, given intradermally in cohorts of patients with biochemically relapse prostate cancer, using a fixed dose-escalation schema every 21 days to establish the MTD.

5.1 Overall Study Design and Plan Description

Figure 1: Dose-escalation study design (3+3 schema)

Following informed consent and screening, archived prostate tumor tissue and patient serum will be tested for the expression of HAAH. Patients who test positive for HAAH expression in either archived tumor tissue or fresh serum may be continued in the study. Baseline biochemical testing (chemistry, complete blood count [CBC], coagulation panel, CH50, and PSA) will be obtained prior to study treatment administration.

Treatment will consist of single repeated doses of SNS-301 administered every 21 days. A traditional 3+3 dose-escalation schema will be used to determine the MTD of SNS-301 for the first 2 doses and a modified dose-escalation schema with 6 patients per dose level for the remaining dose. Planned doses of SNS-301 are 2.0×10^{10} , 1.0×10^{11} and 3.0×10^{11} particles per administration diluted to 1 mL and administered intradermally. Additional patients will be enrolled at the highest dose level until at least 6 patients can be evaluated even if no DLTs are observed at the dose. Planned treatment may continue for two additional doses of SNS-301 administered every 21 days. Serum and whole blood samples will be obtained on the day of study treatment administration (Day 1) and 21 days thereafter. In patients who continue to receive study treatment, biochemical and immunologic testing will continue every 21 days.

The MTD will be determined over the first 21-day interval following a single dose of SNS-301 in 3 consecutive dose cohorts. The MTD will be considered the dose level lower than that dose which produces ≥ 2 DLTs in 3 or 6 patients. A DLT will be considered a protocolspecified drug-related grade 3-4 (National Cancer Institute Common Terminology Criteria for Adverse Events [NCI-CTCAE] V 4.03) adverse experience) (Section 5.4.5.1). The RP2D will be the highest dose administered if no MTD is observed.

Dose cohorts will be enrolled sequentially.

An evaluation period of at least 21-days for the first patient (sentinel patient) in a new cohort is required to evaluate tolerability before adding additional patients to the cohort. If safety/tolerability is adequate, then the remaining patients will be dosed in the cohort. A second evaluation will occur for the last patient of each cohort of at least 21-days to evaluate safety/tolerability before dose escalation to the next cohort will occur. Enrollment will be held if an administration site reaction (ASR) of grade 3 or greater (NCI-CTCAE V4.03) is observed until the event resolves. In the event enrollment is held for an ASR, the Sponsor, Medical Monitor and PI will evaluate the outcome of the ASR and must agree to continued enrollment.

Dose-escalation will proceed once all patients in a cohort (unless the MTD is observed) have completed a 21-day safety evaluation following the first dose of study treatment in the cohort. Planned treatment may continue for an additional 2 extra doses of SNS-301 administered every 21 days. Additional patients will be enrolled at the highest dose level until at least 6 patients can be evaluated even if no DLTs are observed at the dose. In patients who tolerate SNS-301, additional treatment may be continued with single doses of SNS-301 at their current dose level, to maintain geometric mean titer (GMT) of HAAH antibodies to no less than 4 times the baseline value for at least six months (9 injections). Treatment will be terminated with the 9th injection or will otherwise be terminated at any time upon the observance of PSA doubling < 90 days or occurrence of unacceptable toxicity as determined by the Investigator (either for that patient or in their dose cohort). After termination, patients will be followed for an additional 6 months with monthly PSA levels and imaging studies as needed.

Once the MTD/RP2D is determined, patients receiving ongoing treatment may be escalated to that dose for subsequent treatments and receive a maximum of 9 injections. Patients who have received more than 9 injections due to the timing of the amendment limiting therapy to 6 months (9 doses), will be stopped at their last dose received and be followed for 6 months as with other patients. These subjects will continue to be followed for safety and biochemical PSA monitoring on a monthly basis for 6 months and are eligible to resume SNS-301 in case of increases in PSA doubling to < 90 days or other evidence of disease progression and decline in immunological parameters.

Pharmacodynamic:

Exploratory pharmacodynamic (PD) analysis will be performed using dose, vaccine-specific antibody response (geometric mean titer), antigen-specific T and B cell indices, and the relative expression of HAAH in each patient's tumor. The PD will be balanced and optimized to the degree of antigen-specific immune response and minimized for the production of regulatory immune processes.

Other Safety:

Safety endpoints will be evaluated by the incidence and severity of administration site reactions, changes in biochemical safety measures, general incidence and types of AEs, serious adverse events (SAEs), and other overt toxicities.

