5.2.4 Enrollment Holds

Enrollment will be held if the subject experiences a grade 3 or greater ASR as determined by the Investigator. The subject must be withdrawn from the study if they experience a grade 3 ASR. Enrollment can be re-started after agreement between the Principal Investigator, Medical Monitor, and the Sponsor.

Study enrollment will be halted in the event of a death of a subject while on the study or within a 30-day period follow study drug exposure regardless of drug relationship. In the event the enrollment is halted, a clinical review of the subject case will be made by the Principal Investigator, Medical Monitor, and the Sponsor to assess the safety of the medicinal product. If the review concludes there is no association of the death with the study drug, restarting enrollment may proceed.

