5.3.5.1 Dose-limiting toxicities

Any of the following, if judged to be associated with SNS-301 (i.e., possibly-, probably-, or definitely related to), will be considered a DLT which are based on the NCI-CTCAE V4.03 criteria:

- 1) Grade 4 non-hematological toxicities (excluding alopecia) of any duration
- 2) Grade 3 non-hematologic (non-laboratory) toxicity lasting > 3 days despite optimal supportive care
- 3) Any Grade 3 or Grade 4 non-hematologic laboratory value if: a). Medical intervention is required to treat the subject; b), the abnormality leads to hospitalization; c). The abnormality persists for >1 week.
- Grade 4 hematologic toxicity, other than those specified in criteria 5 and 6 below, lasting > 7 days
- 5) Grade 3 or Grade 4 febrile neutropenia of any duration
- 6) Grade 3 thrombocytopenia in combination with a grade 3 or greater blood and lymphatic system disorder
- 7) Grade 3 AST or ALT that is associated with a grade 2 rise in bilirubin

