Signs and symptoms will be graded by the Investigator using the NCI-CTCAE V4.03 graded 1-5. Grade refers to the severity of the AE. For events not described in the NCI CTCAE, the Investigator will assign grades as 1= mild, 2=moderate, 3=severe, 4=life-threatening, and 5=fatal based on this general guideline:

- Grade 1: Mild; asymptomatic or mild symptoms; clinical or diagnostic observations only; intervention not indicated.
- Grade 2: Moderate; minimal, local or noninvasive intervention indicated; limiting ageappropriate instrumental ADL*
- Grade 3: Severe or medically significant but not immediately life-threatening; hospitalization or prolongation of hospitalization indicated; disabling; limiting self-care ADL**.
- Grade 4: Life-threatening consequences; urgent intervention indicated.

Grade 5: Death related to AE. (Grade 5 (Death) may not appropriate for some AEs and therefore may not an option.)

Activities of Daily Living (ADL)

*Instrumental ADL refer to preparing meals, shopping for groceries or clothes, using the telephone, managing money, etc.

**Self-care ADL refer to bathing, dressing and undressing, feeding self, using the toilet, taking medications, and not bedridden.

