This is a Phase I, open-label study of SNS-301, an HAAH (Human aspartyl-asparaginyl- β -hydroxylase)-directed nanoparticle vaccine, given intradermally in cohorts of patients with biochemically relapse prostate cancer, using a fixed dose-escalation schema every 21 days to establish the MTD.

Following informed consent and screening, patient serum will be tested for the expression of HAAH. Patients who test positive for HAAH expression in fresh serum may be continued in the study. Baseline biochemical testing (chemistry, complete blood count [CBC], coagulation panel, total complement activity [CH50], and prostate-specific antigen [PSA]) will be obtained prior to study treatment administration.

Figure 4-1. DOSE-ESCALATION STUDY DESIGN (3+3 SCHEMA)

Treatment will consist of single repeated doses of SNS-301 administered every 21 days. A traditional 3+3 dose-escalation schema will be used to determine the MTD of SNS-301 for the first 2 doses and a modified dose-escalation schema with 6 patients per dose level for the remaining dose (Figure 4-1). Planned doses of SNS-301 are 2.0 x 10^{10} , 1.0×10^{11} and

 3.0×10^{11} particles per administration diluted to 1 mL and administered intradermally. Additional patients will be enrolled at the highest dose level until at least 6 patients can be evaluated even if no DLTs are observed at the dose. Planned treatment may continue for two additional doses of SNS-301 administered every 21 days. Serum and whole blood samples will be obtained on the day of study treatment administration (Day 1) and 21 days thereafter. In patients who continue to receive study treatment, biochemical and immunologic testing will continue every 21 days.

The MTD will be determined over the first 21-day interval following a single dose of SNS-301 in 3 consecutive dose cohorts. The MTD will be considered the dose level lower than that dose which produces \geq 2 DLTs in 3 or 6 patients. A DLT will be considered a protocolspecified drug related grade 3-4 (National Cancer Institute Common Terminology Criteria for Adverse Events [NCI-CTCAE] V 4.03) adverse experience). The recommended Phase 2 dose (RP2D) will be the highest dose administered if no MTD is observed.

Dose cohorts will be enrolled sequentially.

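### No DLT criterion covers a Grade 5 event in its own right, so a drug-related Cycle 1 death with no separately recorded qualifying event is left out of the count that sets the MTD

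*Protocol*

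**What the plan says.** Protocol 5.1 gives the general definition: "A DLT will be considered a protocolspecified drug-related grade 3-4" adverse experience by NCI-CTCAE. SAP section 4 (Study Design) has the same sentence: "A DLT will be considered a protocolspecified drug related grade 3-4".

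The working list of seven criteria appears in the synopsis, in Protocol 5.3.5.1 and in SAP 6.3. Criterion 1 reads "Grade 4 non-hematological toxicities (excluding alopecia) of any duration". Criterion 4 reads "Grade 4 hematologic toxicity, other than those specified in criteria 5 and 6 below, lasting > 7 days". The others also name Grade 3, or Grade 3 or 4. The one open-ended grade is in criterion 6, where it applies only alongside Grade 3 thrombocytopenia.

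The severity scale in Protocol 5.5.3.5 runs from 1 to 5, and its top category is "Grade 5: Death related to AE".

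Three results depend on the DLT definition:
- The MTD is the level below the dose that gives two or more DLTs in 3 or 6 patients (Protocol 5.1).
- One primary endpoint is "Determine the DLTs associated with SNS-301" (Protocol 4.2.1).
- For the default Phase 2 dose, Protocol 5.1 says "The RP2D will be the highest dose administered if no MTD is observed".

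Deaths have their own rule in Protocol 5.2.4. Enrollment halts after any death on study or within 30 days of exposure, and a restart is described for one outcome only: "If the review concludes there is no association of the death with the study drug, restarting enrollment may proceed".

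**The concern.** A DLT definition normally has no upper limit on severity. This one stops at Grade 4, on a scale where a fatal event is Grade 5. The closed range is hard to read as shorthand for that grade or worse, because the same documents use open-ended grades where they intend them: in criterion 6 and in the enrollment hold for administration site reactions.

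The primary result turns on the difference between one event and two in at most six patients. If the most severe outcome adds nothing to the tally, the tally can stay below the threshold when it should have crossed it. The reported list of DLTs would also omit the event that readers most need to see.

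**Working it through.** **Step 1. The plan's own figure.** Three dose levels with at most 6 patients each give 3 × 6 = 18, which matches the stated sample size of about 18. The minimum is 3 + 3 + 6 = 12. The point does not affect either number.

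**Step 2. Each criterion against an event recorded as Grade 5.**

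| Criterion | Grade named | Met by a Grade 5 event? |
|---|---|---|
| 1, non-hematologic | 4 | Not by itself; met if a Grade 4 event was also recorded |
| 2, non-hematologic, non-laboratory | 3, over 3 days | Not by itself |
| 3, non-hematologic laboratory value | 3 or 4, with conditions | Not by itself |
| 4, hematologic | 4, over 7 days | No; death within 7 days of onset also rules out the duration |
| 5, febrile neutropenia | 3 or 4 | Not if graded 5 |
| 6, thrombocytopenia plus another blood or lymphatic disorder | 3, plus 3 or above | Only when Grade 3 thrombocytopenia is also present |
| 7, AST or ALT with bilirubin | 3 with 2 | Not by itself |

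The uncounted set is therefore drug-related Cycle 1 deaths in patients with no separately recorded event that meets a criterion. Two examples are a hematologic event that kills within 7 days and febrile neutropenia graded 5.

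**Step 3. Effect on the count at the top dose.** Let *D* be the number of patients with a listed DLT and *F* the number of other patients who die of a drug-related event with no qualifying record. The written rule counts *D*; the full count is *D* + *F*. The threshold is 2. Protocol 5.3.5 replaces only patients who withdraw in Cycle 1 for reasons other than safety or toxicity, so a patient lost to a related death stays in the denominator.

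| *D* | *F* | Written rule | Full count | MTD finding changes? |
|---|---|---|---|---|
| 0 | 1 | 0/6 | 1/6 | No |
| 1 | 1 | 1/6 | 2/6 | Yes |
| 0 | 2 | 0/6 | 2/6 | Yes |
| 2 or more | any | at least 2/6 | at least 2/6 | No |

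In the rows that change, the written rule finds no MTD and the default RP2D is 3.0×10^11. The full count puts the MTD one level lower, at 1.0×10^11. The ratio is 3.0×10^11 / 1.0×10^11 = 3.

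**Step 4. When this can arise.** Because a death halts enrollment, reaching six patients with an uncounted death requires the death to fall among patients already dosed. Protocol 5.1 allows this: after the sentinel patient's 21 days, the remaining patients in the cohort may be dosed. The synopsis describes a slower start, with the first patient and then two more, which narrows the opportunity without removing it.

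**The case against.** The strongest case against is that related deaths already face a stricter rule than the DLT count. Protocol 5.2.4 stops enrollment at a single death and describes no restart for a related one. Escalation also requires the sentinel review, a completed 21-day evaluation in every patient of the cohort, and a review of the global safety profile. The synopsis lets convincing safety data override the MTD as the RP2D; those data then go to the FDA, and the RP2D is changed or further cohorts are proposed. In addition, the Protocol 5.1 sentence is a summary that points to the criteria list, and most investigators would call a related death dose-limiting.

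Much of this stands. A reader might infer that the plan would allow escalation to continue after a drug-related death; the rules above do not support that. A reader might also infer that every drug-related death goes uncounted. That is too broad, since a death preceded by a recorded Grade 4 non-hematologic event counts under criterion 1, and criterion 6 can catch a fatal blood disorder when Grade 3 thrombocytopenia is present.

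The objection does not repair the count. The halt governs enrollment and leaves the tally among patients already dosed unchanged. The global safety review comes before a dose increase, and there is none after the top level. The RP2D override depends on judgement and changes the recommended dose, not the DLT result. The criteria list has the same upper limit as the summary sentence. SAP 8.6.2 tabulates severity over Grades 1 to 5, so a death would appear in the adverse event tables while being absent from the DLT count.

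**Conclusion.** The point holds as a wording gap in a primary-endpoint definition, and it should be corrected. As written, a drug-related Cycle 1 death without a separately recorded qualifying event adds nothing to the DLT count. The consequence is confined mainly to the top dose and to the reported DLT result. At worst, 1/6 is read where 2/6 is correct, and the default RP2D is three times the MTD that the full count would give.

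That outcome requires a related death among patients already dosed at 3.0×10^11, no qualifying event recorded in that patient, one listed DLT or a second such death among the six, and no use of the RP2D override.

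A reader might infer that a wrong RP2D is likely. The documents do not support that. They give no human DLT or death rate, Protocol 3.2 reports no effect on mortality in the rat study, and patients with distant metastases are not eligible. No probability is attached here. The case rests on the text and the low cost of correcting it.

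**What to change.** In Protocol 5.1 and SAP section 4, change the DLT grade range to 3-5. In the lists in the synopsis, Protocol 5.3.5.1 and SAP 6.3, add one criterion: *any Grade 5 event at least possibly related to SNS-301*. That single line covers hematologic and non-hematologic deaths alike, so criterion 1 needs no rewording.

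The cost is more than editorial. Protocol 7.4 requires a written, signed amendment and IRB notification, with approval where necessary. Protocol 3.4 shows that patients have already been treated, so the change should come with a one-off documented check of Cycle 1 records, for about 18 patients, to confirm whether any past count is affected. No new patients, visits or data are needed, because Protocol 5.5.3.6 already requires every death on study or within 30 days of the last dose to be reported as an SAE.
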